## CONFIDENTIAL

13

possible. The generated gene lists (combination vs. placebo, vitamin E vs. placebo, DHA vs. placebo) will be further analyzed in pathway exploration programs (MetaCore and IPA).

The oxylipin levels will be analyzed similarly to the hepatic fat fraction analysis with a linear mixed analysis of covariance. Additionally, the correlation between the change in oxylipin levels from baseline to 6-month and the change in hepatic fat fraction will be evaluated. Specifically, the Spearman correlation coefficient will be estimated along with a 95% confidence interval for each treatment group.

# 8.5 Post hoc analysis

If a positive intervention effect is indicated based on the primary outcome, the 6-month biomarker levels (i.e. ELF and Pro-C3) will be evaluated with a linear mixed analysis of covariance (ANCOVA) model. Baseline biomarker level, intervention group, and baseline diabetes status will be included as fixed effects. Study site will be included as a random effect. Pairwise comparisons of the combination (DHA EE + vitamin E) vs PBO, vitamin E vs. PBO, and DHA EE vs. PBO will be estimated along with 95% confidence intervals. A Dunnet correction for multiple comparisons will be used.

# 8.6 Safety Analysis

Adverse events (AEs) will be collected and classified according to the Common Terminology for Adverse Events (CTCAE) system. Note that each CTCAE v5.0 term is a MedDRA LLT (Lowest Level Term). All adverse events (AEs) will be summarized by intervention group according to the safety population. The number of subjects experiencing a given event will be summarized overall (i.e. any event of any grade) and by the maximum recorded grade. A separate listing will be provided of the subset of events that were indicated as serious adverse events (SAEs).

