6.2 Schedule of assessments

Hematology*	Х				CBC	Х
Coagulation: INR	Х					
Urine pregnancy test (DipStick)	Х		Х			
Skinner questionnaire ²	Х					
AUDIT questionnaire^	Х			X	X	Х
Vital signs	Х		Х		Х	Х
Lipid panel* including oxidized LDL		x				х
Plasma/serum for inflammatory markers		X				X
Anthropometrics	Х				X	х
RANDOMIZATION			Х			
DHA & α-tocopheryl determination and oxylipins ¹		X			x	X
Product dispense			Х			
Compliance-Pill count				Х	Х	Х
Adverse event reporting		Х	Х	Х	X	X
ConMeds			Х	Х	Х	Х
FFQ	Х		Х	Х	Х	Х
SF-36 questionnaire			Х			Х
Biosample collection -for exploratory analyses and future research use¶		x				x

* fasted blood draw required and ALT, AST, Alk-P, bilirubin is measured 2x;

⁺values obtained at screening (except vital signs and FFQ) will be considered 'baseline' values;

#HAVIgM to be performed unless negative results in past 3 years;

¹oxylipins measured only at V1 and V4.

²Skinner Lifetime Drinking Questionnaire and AUDIT given at V0 Screening

³ Reminder phone calls at months 2,4 and 5are advised to assist with retention and check on subject compliance, no diet fluctuations, ConMeds, and AEs. Only deviations, ConMeds, and AEs are to be recorded in the eCRF from such phone calls.

** Additional time may be allowed between study visits with approval and subsequent protocol deviation.

^ Audit questionnaire - Self-report version is collected at V0, V3 and V4 and the interview is only conducted during the 1month phone call

¶ Refer to lab manual for sample collection table - Exploratory analyses include gene expression at V1 and V4 in a subset of 40 subjects, and PNPLA3, HSD17b, haptoglobin genotyping at V1.

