9.3.5 Safety variables

All SAEs and AEs will be summarized by group. The number of subjects experiencing any events will be examined and the frequency of occurrence by system organ class will be tabulated using Medical Dictionary for Drug Regulatory Affairs (MedDRA) codes.

Vital signs, Hematology, Lipid panel, and Clinical Chemistry data will be summarized using descriptive statistics by group per timepoint including change from baseline at 6 months with group differences analysed using Least Squares Means and 95% Confidence Intervals.

A sub-set analysis will be performed in those with elevated baseline TGs to assess changes with the intervention over 6 months.

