10 SAFETY

10.1 Definitions and Standards

Adverse Event (AE):

Any untoward medical occurrence in a subject involved in a clinical study administered an investigational product, whether or not related to this product.

An AE can therefore be any unfavourable and unintended sign (including an abnormal laboratory finding for example), subjective and objective symptom, or disease temporally associated with the use of a product, accidents, and whether or not considered related to the product or study-related procedure and reported by the subject or observed by the investigator.

Adverse Reaction (AR):

All noxious and unintended responses to a product related to any dose should be considered as AR. ARs are a subset of all suspected AEs for which there is reason to conclude that the investigational product caused the event.

Suspected Adverse Reaction (SAR)

SAR means any AE for which there is a reasonable possibility that the product or clinical trial material caused the AE. A SAR implies a lesser degree of certainty about causality than an AR, which means any AE caused by an investigational product.

Serious Adverse Event (SAE):

Any AE that at any dose fulfils at least one of the following criteria:

- Is fatal (results in death) (note: death is an outcome, not an event)
- is life-threatening

 (note: the term "life-threatening" refers to an event in which the subject was at risk of death at the time of the event; it does not refer to an event which could hypothetically have caused death had it been more severe)
- requires inpatient hospitalization or prolongation of existing hospitalization
 (*note*: "inpatient hospitalization" refers to an unplanned, overnight hospitalization)
- results in persistent or significant disability/incapacity

(*note*: the term means substantial disruption of one's ability to conduct normal life function)

• is a congenital anomaly/birth defect

(*note:* congenital anomaly/birth defect in offspring of subject taking the product regardless of time to diagnosis)

• is medically significant

(*note*: Medical and scientific judgement should be exercised in deciding whether expedited reporting is appropriate in other situations, such as important medical events that may not be immediately life-threatening or result in death or hospitalisation but may jeopardise the subject or may require intervention to prevent one of the other outcomes listed in the definitions above).

Suspected Unexpected Serious Adverse Reaction (SUSAR):

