10.3 Safety Management

10.3.1 Procedures

All AEs occurring during clinical studies are recorded in the eCRF and are classified according to the Common Terminology for Adverse Events (CTCAE) system. AEs should be captured from the screening visit (V1) to the end of the study. Refer to the

https://ctep.cancer.gov/protocolDevelopment/electronic_applications/docs/CTCAE_v5_Quick_R eference_8.5x11.pdf_and_https://livertox.nih.gov/Severity.html, for additional information.

CTCAE Terms

An Adverse Event (AE) is any unfavorable and unintended sign (including an abnormal laboratory finding), symptom, or disease temporally associated with the use of a medical treatment or procedure that may or may not be considered related to the medical treatment or procedure. An AE is a term that is a unique representation of a specific event used for medical documentation and scientific analyses. Each CTCAE v4.0 term is a MedDRA LLT (Lowest Level Term).

CTCAE Grades

Grade refers to the severity of the AE. The CTCAE displays Grades 1 through 5 with unique clinical descriptions of severity for each AE based on this general guideline:

Grade 1 Mild; asymptomatic or mild symptoms; clinical or diagnostic observations only; intervention not indicated.

Grade 2 Moderate; minimal, local or noninvasive intervention indicated; limiting ageappropriate instrumental ADL*.

Grade 3 Severe or medically significant but not immediately life-threatening; hospitalization or prolongation of hospitalization indicated; disabling; limiting self-care ADL**.

Grade 4 Life-threatening consequences; urgent intervention indicated.

Grade 5 Death related to AE. Grade 5 (Death) is not appropriate for some AEs and therefore is not an option.

A Semi-colon indicates 'or' within the description of the grade. A single dash (-) indicates a Grade is not available. Not all Grades are appropriate for all AEs. Therefore, some AEs are listed with fewer than five options for Grade selection.

Definitions

A brief Definition is provided to clarify the meaning of each AE term. A single dash (-) indicates a Definition is not available.

Navigational Notes

A Navigational Note is used to assist the reporter in choosing a correct AE. It may list other AEs that should be considered in addition to or in place of the AE in question. A single dash (-) indicates a Navigational Note has not been defined for the AE term.

Activities of Daily Living (ADL)

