# 3.3 Safety Objective(s)

To examine any treatment-emergent adverse event (TEAEs) and changes in clinical safety laboratory parameters. Safety will be assessed with vital signs, serum hematology and biochemistry, and AE/SAE reporting.

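### The SAP safety section omits the protocol's group comparison for vital signs, hematology and creatinine/eGFR (and probably GGT), and two smaller gaps concern never-dosed subjects and the treatment-emergent rule.

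*SAP*

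**What the plan says.** **Safety variables.** SAP 3.3 gives the objective as "To examine any treatment-emergent adverse event (TEAEs) and changes in clinical safety laboratory parameters" and adds: "Safety will be assessed with vital signs, serum hematology and biochemistry, and AE/SAE reporting". Protocol 9.3.5 asks for descriptive statistics by group and timepoint for vital signs, hematology, lipid panel and clinical chemistry, including "change from baseline at 6 months with group differences analysed using Least Squares Means and 95% Confidence Intervals". Protocol 7.1.3 places GGT, creatinine and eGFR/creatinine clearance in the chemistry panel. SAP 8.6 deals only with adverse events: "All adverse events (AEs) will be summarized by intervention group according to the safety population", overall and by maximum grade, plus a listing of SAEs. In the SAP 12.0 table list, the only tables labelled for safety outcomes are 13.1 (AEs) and 13.2 (SAEs).

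**Safety set.** SAP 6.3 equates the safety population with the ITT population, meaning everyone randomized, and then analyses subjects by the product they actually received. Protocol 9.3.8 requires at least one dose. SAP 6.1 foresees randomized subjects who never start treatment, but provides only an efficacy set (mITT) for that case.

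**Treatment emergence.** Protocol 9.3.5 states "All SAEs and AEs will be summarized by group". Neither it nor SAP 8.6 gives an onset rule. Protocol 10.3.1 says "AEs should be captured from the screening visit (V1) to the end of the study", and the "Adverse event reporting" row of protocol 6.2 is marked at V1 (Day -21 to -5). SAP Table 1, presented as taken from protocol 6.2, leaves V1 blank and begins at V2.

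**The concern.** Protocol 9.3.9 leaves it to the SAP to lay out every analysis that will be run. An analysis that the protocol specifies and the SAP drops is therefore likely not to be produced. Vital signs and hematology are named as safety measures in both documents, so the stated safety objective would be met for them only by unadjusted descriptive statistics.

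The other two gaps concern the AE tables. An as-received grouping cannot place a subject who received nothing. A table of all AEs, with capture possibly starting before dosing, can mix background events into the arm columns and pull a real difference toward no difference.

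**Working it through.** **1. Which protocol 9.3.5 variables get a group comparison in the SAP**

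| Variable | Comparison in SAP | Where |
|---|---|---|
| Lipid panel | Yes | 8.3; Tables 10.1 and 10.2 |
| ALT, AST, ALK-P | Yes | 8.3; Tables 7.1 and 7.2 |
| Total bilirubin | Listed as secondary with the liver tests | 4.2 |
| Glucose, insulin, HbA1c | Yes | 8.3; Tables 3.1 and 3.2 |
| GGT | Only if liver enzymes is read beyond the lists in 4.2 and 8.1 | unclear |
| Creatinine, eGFR | No | none |
| Hematology | No (platelets enter only through FIB-4) | none |
| Vital signs | No | none |

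Precision of the missing comparison, using the planned completers (60/60/30/30) and a two-sample t interval:

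- 60 vs 60: t(0.975, 118) × √(1/60 + 1/60) = 1.980 × 0.1826 = 0.36 SD.
- 60 vs 30: t(0.975, 88) × √(1/60 + 1/30) = 1.987 × 0.2236 = 0.44 SD.

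For systolic pressure with an assumed SD of change of 10 to 15 mmHg (neither document gives one), this is 3.6 to 5.4 mmHg and 4.4 to 6.7 mmHg. These figures show what the omitted estimate could resolve. They do not measure an error.

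**2. One never-dosed subject in the safety set**

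Inputs: arms of 65/65/35/35, a risk ratio of 2.00 among dosed subjects, and no event in the never-dosed subject (assumed). The ratio scales with the denominators:

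- Counted in placebo: 2.00 × 65/64 = 2.03.
- Counted in the combination: 2.00 × 64/65 = 1.97.
- Counted in a single-agent arm: 2.00 × 34/35 = 1.94.
- One in each 65-subject arm: the factors cancel, 2.00.

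**3. Pre-dose events counted in the AE tables**

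V1 capture adds 5 to 21 days before randomization, which is 5/185 = 2.7% to 21/201 = 10.4% of a capture window ending at Day 180.

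Assumptions: placebo on-treatment incidence p0 of 5%, 20% or 30% over 180 days; active incidence 2 × p0; constant background rate r = -ln(1 - p0)/180. Pre-dose probability over d days: p_pre = 1 - exp(-r·d). Observed incidence: 1 - (1 - p_pre)(1 - p_on).

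Worked case, p0 = 20%, d = 21: r = 0.00124 per day; p_pre = 0.0257; active 1 - 0.9743 × 0.60 = 0.4154; placebo 1 - 0.9743 × 0.80 = 0.2206; ratio 1.88.

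| Pre-dose days | Pre-dose rate | Observed ratio, p0 from 5% to 30% |
|---|---|---|
| 5 | full background | 1.97 |
| 21 | full background | 1.89 to 1.88 |
| 5 | half background | 1.99 to 1.98 |
| 21 | half background | 1.94 to 1.93 |
| 1 (assumed for the SAP schedule) | full background | 1.99 |

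**The case against.** **SAP 8.0 already covers these variables.** It promises unadjusted descriptive statistics per measured time point. That can be read to reach vital signs and hematology, but it names no variable or table and specifies no group difference. The missing comparison stands.

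**GGT is a liver enzyme.** SAP 8.3 models liver enzymes and protocol 7.1.3 assays GGT, so GGT may be intended. SAP 4.2 and 8.1 name only ALT, AST, ALK-P and bilirubin. This is ambiguity, and GGT is the softest item.

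**Baselines.** A reader might infer from SAP 8.1, whose list omits these variables, that no baseline is set. That does not hold. The SAP Table 1 footnote makes screening values the baseline except for vital signs and FFQ. Hematology and the rest of the chemistry panel are taken before treatment only at V0. Protocol 6.3.4 takes vital signs at randomization.

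**Blood pressure and heart rate.** A reader might infer a known hemodynamic risk from protocol 1.3.2, which says DHA lowers both. The section presents these as cardiovascular benefits, and the title of the reference cited for blood pressure describes a rat study. The case rests on the protocol's own specification instead.

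**Comparator.** Protocol 9.3.5 does not say versus placebo. That contrast is natural because the SAP uses it elsewhere, but the protocol does not state it.

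**Pre-dose events may not count at all.** Protocol 10.1 defines an AE as "Any untoward medical occurrence in a subject involved in a clinical study administered an investigational product", and SAP Table 1 starts at V2. On that reading dilution is negligible. The documents do not settle the point, so one cannot say that pre-dose events will be in the tables.

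**Never-dosed subjects may not exist.** Product is dispensed at the randomization visit. If everyone takes a dose, the ITT and safety sets contain the same subjects and the table labels do no harm. A reader might infer that AE denominators in general are undefined; only the placement of never-dosed subjects is.

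**Conclusion.** The main point holds on the current text: the SAP drops a protocol-specified safety comparison for vital signs, hematology and creatinine/eGFR, and for GGT on the narrower reading. The omission is partial, since lipids, ALT, AST, ALK-P, glucose, insulin and HbA1c are compared and bilirubin is listed with them. Nothing in the documents shows that a safety conclusion would change. What is lost is an estimate with a half-width of about 0.36 SD (0.44 SD for a single-agent arm), assuming the planned completers.

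The second and third points are real but small and conditional. The safety-set conflict matters only if a randomized subject is never dosed, and one such subject moves a ratio of 2.00 to 1.94 to 2.03. The missing onset rule matters mainly if V1 events are counted. A true 2.0 then shows as about 1.88 to 1.97 at the full background rate, or 1.93 to 1.99 at half that rate, on assumed incidences of 5% to 30% and a constant rate. On the SAP schedule it is 1.99. A reader might infer that a safety signal would be hidden; these figures do not support that.

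The primary efficacy analysis is unaffected. The changes should be made, but the trial does not turn on them.

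**What to change.** 1. **SAP 8.6 and 12.0.** Add LS-mean group differences with 95% CIs in 6-month change for vital signs, hematology, creatinine/eGFR and GGT, with matching tables. Name the contrast; versus PBO fits the rest of the SAP. Use the baselines already set: V0 for hematology and these chemistry items, V2 for vital signs. Comparisons already in SAP 8.3 need not be repeated. If liver enzymes in 8.3 was meant to include GGT, say so there and in 4.2.
2. **SAP 6.3.** Restore the protocol 9.3.8 condition of at least one dose, grouped by product received. Correct the ITT label on Tables 13.1 and 13.2 and the combined ITT/Safety label on Table 1.6.
3. **SAP 8.6.** Define a treatment-emergent AE as one with onset or worsening from first dose to a stated end date. Base the by-arm and maximum-grade tables on these events and list earlier ones separately. Reconcile the V1 entry for AE reporting between protocol 6.2 and SAP Table 1.

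The cost is SAP wording and a few standard tables. All data are already scheduled: vital signs at V2, V3 and V4; clinical chemistry and blood counts at V0, V3 and V4.

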## 8.7 Responder Analysis

A responder will be defined as a relative decrease in hepatic fat fraction (MRI-PDFF) by 30% or higher on the end of treatment MRI as compared to the baseline MRI. The proportion of responders will be estimated, along with a 95% confidence interval, for each intervention group.

# 8.8 Handling of Missing Data

Missing data will not be imputed. Only observed data will be included in the statistical analysis. For a given endpoint, if data is collected during at least 2 post randomization time points, statistical models that account for unbalanced data will be used. Specifically, missing data will be handled by maximum likelihood estimation of mixed models which assumes the data is missing at random.

## 9.0 Deviations from Statistical Plan and Other Issues

During the analysis and reporting process, any deviations from the statistical analysis designed for this protocol will be described and justified in the statistical report.

## 10.0 Data management plan

Data handling and cleaning prior to statistical analysis is outlined in the data management plan Version 2.2 (2017-1088 Data Management Plan Version 2.2\_12Oct2021).

## 12.0 Listing of tables

The following serves as a general guide to the provided tables and figures for the primary and secondary endpoints. Slight variations are possible depending on the data at the time of analysis such as: changing table numbers, re-ordering of tables, or deletion of tables if appropriate.

Table 1.1 Subject disposition:

- a. Number of subjects by visit and treatment arm
- b. Number of subjects by treatment arm and group:
  - i. Screened
  - ii. Randomized
  - iii. Discontinued
  - iv. Completed
- c. Premature discontinuations by reason and treatment arm

Table 1.2 Protocol violations by treatment arm and population

Table 1.3 Compliance by treatment arm and population

Table 1.4 Medical History listing

Table 1.5 Prior and concomitant medications listing

Figure 1 Consort flow diagram

Table 1.6 Demographics (ITT/Safety population)

Table 1.7 Demographics (PP population)

Table 2.1 Hepatic fat fraction [%] - ITT

Table 2.2 Hepatic fat fraction [%] - PP

Table 3.1 HbA1c and insulin resistance measure - ITT

Table 3.2 HbA1c and insulin resistance measure - PP

Table 4.1 SF-36 domains - ITT

Table 4.2 SF-36 domains - PP

Table 5.1 Inflammatory markers - ITT

Table 5.2 Inflammatory markers - PP

Table 6.1 Anthropometric measures - ITT

Table 6.2 Anthropometric measures - PP

Table 7.1 Liver enzymes - ITT

Table 7.2 Liver enzymes - PP

Table 8.1 FIB-4 score - ITT

Table 8.2 FIB-4 score - PP

Table 9.1 Plasma vitamin E and plasma DHA - ITT

Table 9.2 Plasma vitamin E and plasma DHA - PP

Table 10.1 Lipid panel - ITT

Table 10.2 Lipid panel - PP

Table 11.1 Dietary DHA and EPA - ITT

Table 11.2 Dietary DHA and EPA - PP

Table 12.1 SNP Analysis - ITT

Table 12.2 SNP Analysis - PP

Table 13.1 Adverse events - safety population (ITT)

Table 13.2 Serious adverse events - safety population (ITT)

Table 14.1 Responder - ITT

Table 14.2 Responder – PP

Table 15.1 SNP and baseline variable interaction analysis (ITT)

Table 15.2 SNP and baseline variable interaction analysis (PP)

# 12.1 Example tables for primary and secondary endpoints

For all example tables, the descriptive statistics and the model derived estimates may be split into two tables. Any log transformed variables will be back transformed to the original scale.

The following table will be produced for the 6-month outcomes analyzed with the ANCOVA approach. Note that if the table includes multiple outcome variables, a column will be added to identify the specific outcome variable (e.g. insulin resistance measures includes HOMO-IR, fasting glucose, fasting insulin, and HbA1c). Note, a supplemental table will be created to provide descriptive statistics for the absolute and percent change from baseline.

|          |  | РВО | DHA EE +
vitamin E | DHA EE | vitamin E |
|----------|--|-----|-----------------------|--------|-----------|
| Baseline | Ν  |     |                       |        |           |
|          | mean (sd)                                    |     |                       |        |           |
|          | median (min, max)                            |     |                       |        |           |
|          | Q1, Q3                                       |     |                       |        |           |
| 6-Month  | N  |     |                       |        |           |
|          | mean (sd)                                    |     |                       |        |           |
|          | median (min, max)                            |     |                       |        |           |
|          | Q1, Q3                                       |     |                       |        |           |
| ANCOVA   | 6-month Estimate
(95 % CI)⁺               |     |                       |        |           |
|          | Estimated difference
to PBO ++ |     |                       |        |           |
|          | (95% CI)                                     |     |                       |        |           |
|          | p-value*                                     |     |                       |        |           |
|          | adjusted p-value**                           |     |                       |        |           |

\* p-value for the pairwise comparisons to the PBO \*\* Dunnett correction

+ Estimated 6-month value adjusting for baseline

++ Computationally equivalent to the estimated difference from placebo in the change from baseline

|             |                  | РВО | DHA EE +
vitamin E | DHA EE | vitamin E |
|-------------|------------------|-----|-----------------------|--------|-----------|
| Absolute    | N                |     |                       |        |           |
| change from | Mean (sd)        |     |                       |        |           |
| Baseline    | Median (min,max) |     |                       |        |           |
|             | Q1,Q3            |     |                       |        |           |
| Percentage  | N                |     |                       |        |           |
| change from | Mean (sd)        |     |                       |        |           |
| Baseline    | Median (min,max) |     |                       |        |           |
|             | Q1,Q3            |     |                       |        |           |

